2 STUDY DESIGN AND SUBJECT SELECTION

This is an single-arm open label study that will be conducted in subjects with PAD including carotid artery disease. Sixty subjects will be treated with high dose statins for 8 weeks followed by 8 weeks of high dose statin + evolocumab (420mg Q 4weeks x 2 doses) therapy. The laboratory assessments (see section 2.2) will be performed at the screening (baseline), after 8 weeks of high-dose statin therapy, and 24 hr and 8 weeks after high dose statin + evolocumab therapy (see Figure 1).

[figure not shown]

Figure 1.

2.1 Recruitment

Recruitment will occur at the Inova Heart and Vascular Institute. The expected length of the recruitment period is 12 months. If the study conduct (e.g. recruitment rate; drop-out rate; data quality; protocol compliance) does not suggest a proper completion of the trial within the reasonable time frame as agreed upon, the recruitment period may be extended to reach the desired sample size.

2.1.1 Eligibility criteria

- Inclusion criteria
 - History of Peripheral Artery Disease (PAD).
Defined as one or more of the following:
 - Documented history of PAD
 - Previous limb or foot amputation for arterial vascular disease (i.e., excludes trauma),
 - Carotid artery disease (defined as >50% stenosis or prior revascularization)
 - Subject may be of either sex and of any race, and must be >18 years of age
 - Subject agrees to not participate in any other investigational or invasive clinical study for a period of 4 months during the study period
 - Subject must be willing and able to give appropriate informed consent
 - The subject is able to read and has signed and dated the informed consent document including authorization permitting release of personal health information approved by the investigator's Institutional Review Board (IRB)
 - Subjects who are either statin-naïve or already on statin and are willing to be started on high dose (HD) statin therapy:
 - If not on statin→start HD statin therapy (atorvastatin 40mg or rosuvastatin 20mg as according to investigator discretion)
 - If on atorvastatin 40 mg once a day→continue
 - If on lovastatin, pitavastatin, simvastatin, or pravastatin→change to atorvastatin 40 mg once a day
 - If on atorvastatin 80mg once a day→continue
 - If on rosuvastatin 20 to 40mg once a day→continue
 - If on rosuvastatin 10mg once a day→increase to 20mg once a day
- **Exclusion criteria:** Subjects will be excluded from entry if ANY of the criteria listed below are met:
 - Prior use of any PCSK9 inhibition treatment
 - Participation in any investigational study within the last 60 days.
 - Severe renal dysfunction, defined as an eGFR <20 mL/min/1.73 m², or creatinine kinase (CK) level at 10 X ULN at screening.
 - Active liver disease or hepatic dysfunction, defined as AST or ALT >3 x ULN as determined by central laboratory analysis at screening
 - Recipient of any major organ transplant (e.g., lung, liver, heart, bone marrow, renal)
 - Known major active infection or major hematologic, renal, metabolic, gastrointestinal, or endocrine dysfunction in the judgment of the investigator

- Malignancy (except non-melanoma skin cancers, cervical in situ carcinoma, breast ductal carcinoma in situ, or stage 1 prostate carcinoma) within the last 5 years
- Subject has received drugs via a systemic route that have known major interactions with background statin therapy within 1 month before randomization or is likely to require such treatment during the study period (e.g. cyclosporine, clarithromycin, HIV protease inhibitors, gemfibrozil)
- Female subject who is unwilling to use at least 2 effective birth control methods for at least 1 month before screening and 15 weeks after the end of treatment with investigational products, unless the subject is sterilized or postmenopausal
- Subject is pregnant or breast feeding, or planning to become pregnant or to breastfeed during receipt of investigational products and within 15 weeks after the end of study treatment
- Known previous hypersensitivity reaction/s to the investigational products' active components and excipients
- Subjects treated with any anticoagulant
- Patients treated with Prasugrel or Ticagrelor
- Subject likely to not be available to complete all protocol-required study visits or procedures, to the best of the subject's and investigator's knowledge
- History or evidence of any other clinically significant disorder, condition, or disease other than those outlined above that, in the opinion of the investigator, may compromise the ability of the subject to give written informed consent, would pose a risk to subject safety or interfere with the study evaluation, procedures, or completion

** Acceptable methods of contraception (birth control) while taking part in this study are:*

- *Total Abstinence (no sexual intercourse), absence of menstrual periods in women for more than one year after menopause (change of life), sterilization surgery, including tubal ligation (tubes tied) or hysterectomy (removal of the uterus or womb) in women or a vasectomy in men.*
- *Oral contraceptives (birth control pills), intrauterine device (IUD), implantable or injectable contraceptives (Norplant or Depo-Provera), contraceptive patch, vaginal ring or use of condom with spermicide. These methods must be used exactly as directed.*

2.2 Study methods

2.2.1 Blood sampling

Phlebotomy sites will be carefully chosen to minimize risk and platelet activation. After discarding the first 2-3mL of free flowing blood, the blood collection tubes will be filled to capacity and gently inverted 3 to 5 times to ensure complete mixing of the anticoagulant. Tubes containing 3.2% trisodium citrate (n=3) will be used for flow cytometry, light transmittance aggregometry and thrombelastography. Tube containing hirudin will be used for shear-induced platelet aggregation and tubes containing 3.2% trisodium citrate will be used for platelet activation marker analysis.

- **Platelet Aggregation**

Platelet aggregation will be assessed in platelet-rich plasma using a Chronolog Lumi-Aggregometer (model 490-4D) with the AggroLink software package after stimulation with 2 and 5µM ADP, 1.2 mM AA and 4ug/ml collagen.

- **Platelet Activation by Flow cytometry**

Expressions of p-selectin, CD36, LOX-1, basigin (CD147, receptor for glycoprotein VI), and oxLDL on platelets will be assessed by flow cytometry using respective antibodies.

- **Platelet-fibrin clot characteristics by TEG6S**

The TEG6s instrument is a microfluidic fully automated cartridge-based device.

- **Lipid profile and Soluble Biomarkers**

After collection, plasma samples will be frozen at -70°C until analysis by commercially available enzyme linked immunoassay kits and ACL TOP 300 coagulation analyzer. Lipid profile will be assessed by conventional laboratory method and soluble markers such as oxLDL, LOX-1 receptor, fibrinogen, hsCRP, p-selectin, Atherox in plasma by enzyme linked immunoassay.

- Safety Labs including Comprehensive Metabolic Panel (CMP) and Creatine Kinase (CK).

2.2.2 **Urine Sampling**

Ten (10) mL of a spot urine specimen will be collected at baseline, 8 weeks post high-dose statin therapy and 8 weeks post first dose of evolocumab.

- **Urine 11-dh-TxB2 and 8-iso-prostaglandin F2_α**

Urine 11-dh-TxB2 concentrations by AspirinWorks test kit, an enzyme linked immunoassay (ELISA).

Urinary 8-iso-PGF_{2α} analysis by 8-iso-Prostaglandin F2_α ELISA Kit (Cayman Chemical Co. #516351).

3 **STATISTICAL CONSIDERATIONS/DATA ANALYSIS**

3.1 **Primary and secondary endpoints**

Primary endpoint

Relative difference in maximal ADP-induced platelet aggregation between high-dose statin therapy and high-dose statin plus evolocumab therapy

Relative difference = 100 * (baseline on high dose statin value – post high dose statin plus evolocumab value) / baseline on high dose statin value

3.1.1 **Secondary Endpoints**

- Relative differences in AA- and collagen-induced platelet aggregation between high dose statin therapy and evolocumab plus high-dose statin therapy.

- Relative differences in platelet bound p-selectin, oxLDL, soluble LOX-1 receptor, between high dose statin therapy and evolocumab plus high-dose statin therapy.
- Relative differences in lipid profile, oxLDL, soluble LOX-1 receptor, fibrinogen, hsCRP, p-selectin, atherox (soluble markers) between high dose statin therapy and evolocumab plus high-dose statin therapy.
- Relative differences in platelet-fibrin clot characteristics and shear-induced platelet aggregation between high dose statin therapy and evolocumab and high-dose statin therapy
- Relative differences in ABI between high dose statin therapy. and evolocumab and high-dose statin therapy
- Relative differences in urinary 11-dh-thromboxane B2 levels between high dose statin therapy and evolocumab plus high-dose statin therapy.
- Relative differences in urinary 8-iso-Prostaglandin F2 α levels between high dose statin therapy and evolocumab plus high-dose statin therapy.

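### The two urinary secondary endpoints have no stated correction for urine dilution and no stated analysis scale

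*Combined protocol and SAP*

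**What the plan says.** Section 2.2.2 (Urine Sampling): "Ten (10) mL of a spot urine specimen will be collected at baseline, 8 weeks post high-dose statin therapy", with a further specimen 8 weeks after the first evolocumab dose. Table 1 places these at Visits 1, 2 and 5. No timed or first-void collection is requested.

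For the thromboxane metabolite the measured quantity is a concentration: "Urine 11-dh-TxB2 concentrations by AspirinWorks test kit". For the isoprostane the section names only the kit, "ELISA Kit (Cayman Chemical Co. #516351", without units or a denominator.

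Section 3.1.1 lists as secondary endpoints "Relative differences in urinary 11-dh-thromboxane B2 levels between high dose statin therapy and evolocumab plus high-dose statin therapy" and, in the same form, "Relative differences in urinary 8-iso-Prostaglandin F2"α. The formula is given under the primary endpoint in section 3.1 and begins "Relative difference = 100 * (baseline on high dose statin value"; the statin plus evolocumab value is subtracted and the result divided by the statin-only value. I take it to apply to the secondary endpoints as well. A positive value means a fall in the marker and a negative value a rise.

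Section 3.2 offers a paired test or a Wilcoxon signed-rank test after a normality check. It does not say whether the test is run on raw values, percentages or logs. No section mentions urinary creatinine, specific gravity, osmolality or any other adjustment for dilution. The metabolic panel in Table 1 is listed as a safety test and is not described as a urine correction.

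**The concern.** The concentration of a substance in a spot urine depends on how much is excreted and on how much water it is excreted in. Only the first is of interest here. If the second is not removed, it enters both the Visit 2 and the Visit 5 value and widens the within-patient comparison. The Visit 2 value is also the denominator of the percentage change, so a dilute Visit 2 sample can produce a very large apparent increase.

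Both markers are named in the secondary objective. Section 1.3 says that nothing is known about PCSK9 therapy and these two markers, so there is no earlier result against which a misleading one would stand out. A real fall could be missed, or an average percentage change could point the wrong way.

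**Working it through.** **1. The plan's own figure.** The only power calculation (section 3.2) is for ADP-induced aggregation: difference 14, SD 30, n = 50, two-sided alpha 0.05. The noncentrality is (14/30) × √50 = 3.30. The normal approximation gives Φ(3.30 − 1.96) = 91.0%; the exact paired t gives 89.9%. For dropout, 50/(1 − 0.16) = 59.5, rounded up to 60. The figure reproduces, but it says nothing about the urinary markers. Only n = 50 is carried forward.

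**2. Inputs that the documents do not give (assumptions).** Marker log-SD 0.4 per visit, independent between visits; dilution log-SD s = 0.3, 0.5 or 0.7 per spot sample; between-visit correlation of dilution ρ = 0 or 0.5; true fall 20%. Perfect dilution correction is represented by s = 0.

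**3. Precision on the log scale.** The SD of the within-patient log ratio is √[2 × 0.4² + 2s²(1 − ρ)]. The noncentrality is −ln(0.8) × √50 / SD, with −ln(0.8) = 0.223. Example for s = 0.5 and ρ = 0: SD = √(0.32 + 0.50) = 0.906, noncentrality 1.74. Power is from the paired t with 49 degrees of freedom.

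| s | SD, ρ = 0 | Power, ρ = 0 | SD, ρ = 0.5 | Power, ρ = 0.5 |
|---|---|---|---|---|
| 0 | 0.566 | 78% | 0.566 | 78% |
| 0.3 | 0.707 | 59% | 0.640 | 68% |
| 0.5 | 0.906 | 40% | 0.755 | 54% |
| 0.7 | 1.140 | 27% | 0.900 | 40% |

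Simulation agrees to within about one point.

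**4. Sensitivity to the marker's own noise.** Let s_b be the non-dilution SD of the log ratio, and give dilution as a CV, where squared log-SD = ln(1 + CV²). Dilution is again independent between visits.

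| Dilution CV | Power, s_b = 0.3 | Power, s_b = 0.5 |
|---|---|---|
| 0 | 99.9% | 87% |
| 20% | 96.5% | 77% |
| 30% | 85.5% | 66% |
| 50% | 56% | 46% |
| 80% | 32% | 29% |

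The loss is modest at a CV of 20–30% if the marker itself is stable, and severe at 50% or more.

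**5. Mean of the percentage change when nothing has changed.** For a lognormal ratio the expected relative difference is 100 × [1 − exp(SD²/2)], that is 100 × {1 − exp[0.16 + s²(1 − ρ)]}.

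| s | Dilution alone, ρ = 0 | Marker noise plus dilution, ρ = 0 | Dilution alone, ρ = 0.5 | Marker noise plus dilution, ρ = 0.5 |
|---|---|---|---|---|
| 0 | 0% | −17% | 0% | −17% |
| 0.3 | −9% | −28% | −5% | −23% |
| 0.5 | −28% | −51% | −13% | −33% |
| 0.7 | −63% | −92% | −28% | −50% |

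The first row matters: with dilution fully removed, averaging percentages still gives −17%.

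**6. Which test is affected.** In 20,000 simulated trials with no true effect and s_b = 0.3, a t-test on per-patient percentages falsely shows a rise in 13.9% of trials without dilution noise and in about 50% at a dilution CV of 50%. A paired t-test on raw concentrations (between-patient log-SD 0.6 assumed) keeps its two-sided type I error at 3.9–4.8% across CVs of 0 to 80%. Its power for a true 20% fall drops from 98.9% at CV 0 to 71%, 40% and 20% at 30%, 50% and 80%.

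**The case against.** The plan does not say that raw values will be analysed. For 11-dh-TxB2 it says concentration; for 8-iso-PGF2α it names a kit and nothing more, and how either kit's result is expressed is not described. A reader might infer that both markers are certainly compared uncorrected. The text supports that for the first marker, while for the second it is an inference from silence. This stands, and the fix allows for it.

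A reader might also infer that dilution swamps these endpoints. Every variability figure above is assumed, and the answer moves with it. At a CV of 20–30% with a stable marker, most of the power remains. Samples from the same patient may also be similarly dilute at both visits, which reduces the loss. This stands too.

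Finally, a reader might infer that dilution as such biases the comparison. Random dilution does not bias a paired test on raw values or the mean log ratio; a bias there would need a systematic change in hydration between Visits 2 and 5, which nothing in the documents indicates. The shift in the mean percentage arises from averaging ratios with a noisy denominator. Creatinine alone would not remove it, whereas the log ratio removes it even without creatinine. Section 3.2 does not commit to testing percentages, so the inflated false-rise rate is conditional. What the objection leaves untouched is the loss of precision under every analysis, and the shift if the endpoint of section 3.1.1 is summarised as a mean.

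**Conclusion.** The gap is real and limited to two secondary endpoints. The plan specifies untimed spot urine, a concentration for one marker, no dilution correction for either and no analysis scale.

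Under the assumptions in step 2, uncorrected dilution lowers power for a 20% fall from about 78% to between 59% and 27% if dilution is independent between visits, or to between 68% and 40% at a correlation of 0.5. The 78% is an upper bound on what correction can achieve, because it assumes that creatinine removes all dilution noise and adds none.

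If percentage changes are averaged or tested, the mean is also shifted towards an apparent rise, against the trial's hypothesis: about −17% from the assumed marker noise alone, with dilution adding to it. The documents support neither the claim that dilution must dominate these endpoints nor the claim that it biases every analysis of them. The primary endpoint and the sample size are unaffected.

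**What to change.** Measure creatinine in the same 10 mL specimen. In section 2.2.2 and the two urinary bullets of section 3.1.1, define both endpoints as analyte per mg creatinine. Analyse the within-patient log ratio of Visit 5 to Visit 2 and report it as a geometric mean percentage change with its confidence interval. If the laboratory already reports results per creatinine, say so and change only the analysis scale. Settle this before the specimens are used up or results are seen.

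The cost is about 180 routine assays (60 patients × 3 visits) on urine already due to be collected, plus a wording change; no visit or procedure is added. One downside remains: the ratio also carries any true change in creatinine excretion.

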3.2 Statistical calculations

Categorical variables will be compared using χ^2 test or the Fisher exact test whereas continuous variables will be assessed using either paired test or Wilcoxon signed rank test after checking for normal distribution. Analyses will be performed with SPSS software (SPSS, Inc., Chicago, IL) and $p < 0.05$ will be considered a significant difference between high-dose statin therapy and evolocumab plus high-dose statin therapy.

[figure not shown]
No prior data is available regarding direct antiplatelet effects of evolocumab. Sample size calculation is mainly based on our previous experience in pharmacodynamic studies. In this study, 50 patients are needed to detect the absolute difference of 14% (~20% relative difference) in ADP-induced aggregation after evolocumab plus high dose statins compared to previous high dose statin therapy alone in these same patients with a power of 91%, a two sided alpha = 0.05 and SD of 30%. Assuming a 16% drop out rate, we need 60 patients in total. Calculations based on a paired t-test.

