7.2 Visit 2: HD statin + evolocumab 420mg Q 4 weeks therapy

7.2.1.1 Subjects will return to clinic for lab measurements (see section 2.2, blood and urine sampling) after 8 weeks (\pm 5 days) of HD statin therapy. Lab measurements will be obtained prior to first dose administration of evolocumab therapy.

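### The primary endpoint is a relative difference, but the 91% power was calculated for the absolute difference, and the plan does not say which is tested

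*Combined protocol and SAP*

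**What the plan says.** Section 3.1 names the primary endpoint: "Relative difference in maximal ADP-induced platelet aggregation between high-dose statin therapy and high-dose statin plus evolocumab therapy". The formula below it takes the on-statin value minus the post-evolocumab value, times 100, and divides by the on-statin value: "post high dose statin plus evolocumab value) / baseline on high dose statin value". The secondary endpoints in 3.1.1 are all worded as relative differences too.

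The denominator comes from Visit 2. Section 7.2 says "Lab measurements will be obtained prior to first dose administration of evolocumab therapy", and no replicate or averaging is described.

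Section 3.2 sizes the trial on another quantity: "50 patients are needed to detect the absolute difference of 14% (~20% relative difference) in ADP-induced aggregation", "with a power of 91%, a two sided alpha = 0.05 and SD of 30" percent. It adds "Calculations based on a paired t-test" and "Assuming a 16% drop out rate, we need 60 patients in total". No SD is given for the percent change.

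For the analysis, 3.2 says that "continuous variables will be assessed using either paired test or Wilcoxon signed rank test after checking for normal distribution". It does not say whether the test is run on the percent differences or on the two raw values. Nor does 3.1 say which post-dose sample enters the formula. Table 1 has blood sampling at Visit 3 (24 hours after the first dose) and at Visit 5 (8 weeks after it).

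**The concern.** An absolute change and a per-patient percent change are different quantities with different sampling behaviour. The percent change is asymmetric: a patient who goes from 40 to 80 scores -100%, and one who goes from 80 to 40 scores +50%. If the two visits differ only by noise, these do not cancel, and the mean comes out negative, as an apparent rise in aggregation. Patients whose Visit 2 value happens to be low carry most weight.

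At stake is whether a real 20% reduction could be missed by a trial that believes it has 91% power. Because the tested scale is not fixed, the choice between a percent-scale and a raw-scale test could also be made after the data are seen. The choice between t-test and Wilcoxon after a normality check adds a second such option.

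**Working it through.** **Inputs from section 3.2.** Absolute difference 14; relative difference about 20%; SD 30; two-sided alpha 0.05; n = 50 evaluable; dropout 16%; paired t-test. The implied mean on-statin value is 14/0.20 = 70.

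**Assumptions not in the documents.** The SD of 30 is the SD of the paired difference; the share of it that is visit-to-visit noise; a between-patient SD of 10 to 20; and the shape of the distribution (lognormal, or normal with values bounded below at 5 or 10 and above at 100).

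**1. The plan's own figure.** 14/30 × √50 = 3.30. Normal approximation: Φ(3.30 - 1.96) = 91.0%. Exact noncentral t with 49 df: 89.9%. Dropout: 50/0.84 = 59.5, so 60. The stated figures reproduce on the absolute scale. If 30 were instead the SD of a single value, the same power would need a pre-post correlation of about 0.5.

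**2. When the conversion to about 20% would be harmless.** If every patient's denominator were 70, the percent change would have SD 30/0.7 = 43 and no bias. Power would then be 90% again. The question is what a varying, noisy denominator does.

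**3. Bias by hand.** Take all of the SD of 30 as equal, independent noise at the two visits. The noise SD per visit is 30/√2 = 21.2, the CV is 21.2/70 = 0.303, and CV² = 0.092.
- No true change: E[(pre - post)/pre] ≈ -CV², or about -9 points.
- True 20% reduction: 1 - 0.80 × 1.092 = 0.126, or about +13 points instead of +20.

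**4. Simulation of the per-patient percent change, n = 50, with the paired SD all noise.** A false increase is a significant t-test result in the wrong direction when nothing changes (nominal 2.5%).

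| Paired SD | Mean shift, no change | False increase | t-test power, true 20% fall |
|---|---|---|---|
| 30, lognormal | about -9 | 22-23% | 62-64% |
| 30, bounded normal | -15 to -22 | 17-22% | 16-26% |
| 20, both shapes | -4 to -8 | about 12% | 66-99% |
| 15, both shapes | -2 to -4 | about 9% (lognormal) | 91-100% |
| 10, both shapes | -1 to -2 | about 6% (lognormal) | at least 99% |

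At SD 30, Wilcoxon on the percent change has power of 82-83% (lognormal) or 57-63% (bounded). It is also pulled the wrong way, with false increases in about 8-11% of trials. In the same SD 30 data, the paired t-test on the absolute change has power of about 87-95%. The ratio of group means stays within about 0.3 points of zero when nothing changes.

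**5. Same SD of 30, but mostly differing response.** With noise SD 5-7 per visit, between-patient SD 10-15 and no upper bound on values, the no-change shift is about -0.6 to -1.2 points and false increases occur in about 3% of trials. Power on the percent change is about 84-87%, against 89-90% on the absolute change. With noise and differing response sharing the variance equally, power on the percent change is about 59%.

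**The case against.** The strongest reply is that the plan never says the individual percent differences are averaged or tested. Section 3.2 speaks of a paired test on continuous variables and sizes the trial on the absolute difference. On that reading the raw paired values are tested and the percent is only a summary. The power then reproduces, the test is unbiased, and a percent taken from group means is nearly unbiased too. This stands as a possible reading, but it leaves a gap: the p-value would test a different quantity from the endpoint named in 3.1. The formula is also written in terms of values, not means, and paired or signed-rank tests need one quantity per patient. Applying the formula per patient is therefore the more direct reading, although it remains an inference.

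The second reply is that the size of the loss depends on a noise split and a distribution that the documents do not give. This stands in full. A reader might infer from the bounded-normal results that the trial's true power is about 20%. The documents do not support that: the lognormal case gives over 60% with the same noise, and the loss is small when noise is small or when most of the SD is differing response.

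A reader might also infer that the formula could produce a false claim of benefit. It could not by this route, since the shift is toward an apparent increase in aggregation.

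**Conclusion.** The point holds as a mismatch that needs no simulation: the named primary endpoint is relative, the 91% power is for the absolute difference, and the tested scale is not stated.

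The consequence is conditional. If per-patient percent differences are tested and the SD of 30 is all visit-to-visit noise around a mean of 70, then:
- the no-effect shift is about -9 to -15 points or more;
- a false increase is declared in about 20% of trials;
- power is about 16-64% by t-test or 57-83% by Wilcoxon, against about 87-95% for absolute change.

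At a paired SD of 20, the shift is about -4 to -8 points and t-test power about 66-99%. At SD 15 or less, or if the SD is mostly differing response, the loss of power is small. If raw values are tested, power is about 90-91%, but the test does not address the endpoint as defined.

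This should be fixed. It does not show that the trial is underpowered, because the calculation is sound for the quantity it used.

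**What to change.** Reword sections 3.1 and 3.2 before analysis:
- Make the tested primary quantity the within-patient absolute change in maximal ADP-induced aggregation, in percentage points, from Visit 2 to one named post-dose visit.
- Test it with the paired t-test that the sample size already assumes. Make Wilcoxon a fixed sensitivity analysis, not an alternative chosen after a normality check.
- Report the percent change as a derived summary, the mean change divided by the Visit 2 mean, with a confidence interval. Do not use the mean of individual percent changes.
- State for the secondary endpoints in 3.1.1 which scale is tested. A log-scale analysis of skewed markers is optional.

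The cost is wording only. No patients, samples or visits are added, and the endpoint then matches the existing power calculation. The small downside is that the headline percent change becomes a group-level figure and no longer an average of individual responses.
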